	
Endpoint 1 (Primary Endpoint): Percentage of subjects without a clinically significant increase in RLS symptoms (i.e. CGI-I score of 5 or less relative to baseline) during the first Phase involving an opioid dose reduction of $\geq 20\%$ relative to baseline.
 
Endpoint 2: Percentage of subjects without a clinically significant increase in RLS symptoms (i.e. CGI-I score of 5 or less relative to baseline) during the first Phase involving an opioid dose reduction of $\geq 1/3$ relative to baseline.
 
Endpoint 3: IRLS during the first Phase with an opioid dose reduction of $\geq 20\%$ relative to baseline.
 
Endpoint 4: IRLS during the first Phase with an opioid dose reduction of $\geq 1/3$ relative to baseline.
 
Endpoint 5: Maximal percentage reduction in opioid dose relative to baseline associated with a CGI-I score of 5 or less, averaged across subjects.
 
Safety
 
Endpoint 1: Frequency of Grade 2 or higher NPNS-related adverse events.
 
Endpoint 2: Frequency of Grade 3 or higher NPNS-related adverse events.
 
Endpoint 3: Percentage of subjects who are discontinued from study due to non-RLS opioid withdrawal symptoms prior to the Extension Phase.
 
NPNS tolerability
 
Percentage of subjects who withdraw from study prior to the Extension Phase citing lack of tolerability of NPNS as the primary reason for withdrawal.
 
Compliance
 
Frequency of device usage on nights with RLS symptoms during Assessment periods during Phase 1 and Phase 2.

Additional Study Assessments (as appropriate)	
 • Weekly assessment of opioid withdrawal symptoms (investigator may employ participant interview and/or COWS scale, as appropriate) • IRLS during run-in week • Nightly subject diary, including RLS symptoms and device usage • Automated compliance tracking – usage data collected via NTX device • Medication use assessment • Subject demographic/characterization assessment • Medication history • Follow-up questionnaire • Leg movement data collected via NTX device

CONFIDENTIAL

All information contained in this document is confidential and is the sole property of Noctrix Health, Inc.
 Any reproduction in part or whole without the written permission of Noctrix Health, Inc. is prohibited.

 NOCTRIX HEALTH	Clinical Trial	Document #: CT-2 (Previously CT-03) Rev: 4.0 (Superseded Rev C) CC#: 720 (Previously DCO #138) Effective: 09/24/2021

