6.2. Risks associated with study procedures

6.2.1. Opioid withdrawal procedure

Opioid withdrawal symptoms can occur during dosage reduction, specifically for rapid dosage reduction of short-acting, high-dose opioids. In contrast, the protocol here involves gradual dosage reduction (approximately 25% per week) of primarily long-acting (e.g. methadone, oxycodone), and exclusively low-dose (below 60 MME) opioids. Therefore, we expect a low risk of opioid withdrawal symptoms. However, it is possible that one or more symptoms that are associated with opioid withdrawal [11] may occur, such as the following: agitation, restlessness, and anxiety, depression, insomnia, yawning, increased tearing or watery eyes, runny nose, sweating, shivering, trembling, or goosebumps, muscle aches or joint pain, nausea or vomiting, abdominal cramps, diarrhea. Subjects will undergo a weekly investigator assessment and subjects with clinically significant withdrawal symptoms will be excluded from further participation. Moreover, subjects with intolerable withdrawal symptoms will have the option to discontinue participation at any time and revert to their original opioid dosage.

7. Adverse Events

Anticipated observations (e.g. common treatment effects) and adverse events occurring during the study will be recorded. Descriptions of anticipated observations and AEs will include the date of onset, the date it ended, the severity, the relationship to study device, and the outcome. All reported AEs will be summarized by the number of subjects reporting AEs, system organ class (where applicable), severity, seriousness, and relationship to study device.

The study Investigator and Coordinator will evaluate, characterize and record in the Case Report Form (CRF) all adverse events (AEs) occurring in all subjects from the time of enrollment to study exit (or premature withdrawal). Adverse events unresolved at study exit will be followed by the Investigator until resolution occurs or at least 60 days after the subject's participation in the study is complete. AEs may be reported spontaneously by the subject or detected by the Investigator or Coordinator. AEs should be evaluated for diagnoses not just symptoms (i.e., "angina", not "chest pain").

CONFIDENTIAL

All information contained in this document is confidential and is the sole property of Noctrix Health, Inc.
Any reproduction in part or whole without the written permission of Noctrix Health, Inc. is prohibited.

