13.2 Run-in and Assessment periods

[figure not shown]
Each Phase involves a 1-2 week run-in period followed by a 1-week assessment period. Assessment periods are primarily designed for endpoint evaluation. Run-in periods are designed for two reasons: (i) to provide a run-in phase to optimize instructions for NPNS device self-administration (e.g. timing and intensity) and (ii) so that any opioid withdrawal symptoms unrelated to the RLS condition resolve prior to the assessment period. Each run-in period will last a minimum of 1-week and a maximum of 2-weeks.

The investigator is permitted to adjust the instructed schedule of opioid medication and/or NPNS usage during a Step-Down based on clinical evaluation of response to opioid treatment and NPNS.

CONFIDENTIAL

All information contained in this document is confidential and is the sole property of Noctrix Health, Inc.
Any reproduction in part or whole without the written permission of Noctrix Health, Inc. is prohibited.

Figure 1. Flowchart of Run-in and Assessment periods for Phases 1 & 2

Additionally:

[figure not shown]
- If clinically significant opioid withdrawal symptoms unrelated to RLS become intolerable during the run-in period for a given Phase, participation will be discontinued and data from the subject will not count towards the efficacy endpoints for that Phase.
- If opioid withdrawal symptoms related to RLS become intolerable at any point during a run-in period, participation will be discontinued and the subject will count towards the efficacy endpoints for that Phase.
- The investigator may decide that participation should be discontinued at any time if there are excessive opioid withdrawal symptoms, even if those symptoms are tolerable.
- If opioid withdrawal symptoms become intolerable mid-week during a run-in period, participation will be discontinued.
- In all cases, efficacy outcome measures CGI-I and IRLS will be assessed at study exit but will not be included in analysis of the efficacy endpoints unless opioid withdrawal symptoms related to RLS was the primary reason for discontinuation.
- The Extension Phase is optional and requires approval by both the investigator and the participant. The structure of this phase is similar phases 1 and 2.

CONFIDENTIAL

All information contained in this document is confidential and is the sole property of Noctrix Health, Inc.
 Any reproduction in part or whole without the written permission of Noctrix Health, Inc. is prohibited.

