17.1.3. Efficacy Analysis

Endpoints 1 and 2 are calculated with the following formula, respectively for Phases 1 and 2:

$100\% * ((X - Y) / (N - M))$, where

- N = Number of subjects who entered the Run-in period for the Phase.
- M = Number of subjects excluded during Run-in period due to non-RLS opioid withdrawal symptoms.
- Y = Number of subjects excluded during Run-in period primarily due to intolerable RLS symptoms.
- X = Number of subjects who complete Assessment period with no clinically significant worsening in Clinical Global Impression-Improvement scale (CGI-I) relative to Baseline, where a clinically significant worsening is defined by a score of 6 (Much worse) or 7 (Very much worse).

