17.1.5. Criterion for Success

If Endpoint 1 is greater than 50 percent, then the study will pass the Primary Efficacy endpoint.

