17.3. NPNS Tolerability

NPNS tolerability will be quantified based on the percentage of participants who voluntarily withdraw from the study prior to the Extension Phase citing lack of tolerability of NPNS treatment as the primary reason for withdrawal, as quantified by selection of response #3 on a questionnaire similar to the one below.

Primary reason for withdrawal:

- I want to return to my original opioid dosage because:
 - (1) my RLS symptoms have gone up after I reduced my opioid dosage
 - (2) I experienced other opioid withdrawal symptoms after I reduced my opioid dosage
- (3) Use of the NPNS devices was uncomfortable or otherwise intolerable
- (4) Other

CONFIDENTIAL

All information contained in this document is confidential and is the sole property of Noctrix Health, Inc.
 Any reproduction in part or whole without the written permission of Noctrix Health, Inc. is prohibited.

 NOCTRUX HEALTH	Clinical Trial Investigational Plan, Protocol CT-03 (Opioid Reduction Study)	Document #: CT-2 (Previously CT-03) Rev: 4.0 (Superseded Rev C) CC#: 720 (Previously DCO #138) Effective: 09/24/2021
---	---	---

The criterion for success will be fewer than 20% of subjects who begin NPNS treatment withdrawing for this reason.

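### The recorded cause of a run-in exit decides whether it is deleted or counted as a failure, so a subject with exit CGI-I 6 or 7 can leave the primary denominator

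*Combined protocol and SAP*

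**What the plan says.** Section 17.1.3 computes Endpoints 1 and 2 as 100% × (X − Y)/(N − M). The denominator starts from "N = Number of subjects who entered the Run-in period for the Phase". What is taken out of it is "M = Number of subjects excluded during Run-in period due to non-RLS opioid withdrawal symptoms", while the term subtracted from the numerator is "Y = Number of subjects excluded during Run-in period primarily due to intolerable RLS symptoms". X counts those who finish the assessment week without a CGI-I of 6 or 7.

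Section 13.2 makes the same split in words: a run-in exit for intolerable withdrawal symptoms that have nothing to do with RLS does not count for that Phase, and one for RLS-related withdrawal symptoms does. It adds "In all cases, efficacy outcome measures CGI-I and IRLS will be assessed at study exit", but then keeps those scores out of the efficacy analysis unless RLS-related symptoms were the main reason for stopping.

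On telling the two causes apart:
- Section 6.2.1 lists possible withdrawal symptoms, among them "agitation, restlessness, and anxiety, depression, insomnia". Section 1 describes RLS patients as often complaining mainly that they cannot fall asleep.
- The synopsis says of the weekly withdrawal assessment that the "investigator may employ participant interview and/or COWS scale, as appropriate". No cut-off is given.
- The form in section 17.3 separates response 1 (RLS symptoms rose) from response "2) I experienced other opioid withdrawal symptoms after I reduced my opioid dosage". The plan uses it only for NPNS tolerability and only for voluntary withdrawals.

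The success rule in section 17.1.5 is "If Endpoint 1 is greater than 50 percent, then the study will pass the Primary Efficacy endpoint". The primary study enrolls 20 to 40 subjects and is open-label (section 14).

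**The concern.** A run-in exit is either a failure or absent from the endpoint, and only its attributed cause decides which. The plan treats the two causes as separable. It does not say who separates them, from what source, or how a mixed picture is resolved. Sleeplessness and restlessness after a dose reduction could fall under either.

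The more serious point is a stated rule. The plan defines failure as CGI-I 6 or 7 and collects CGI-I at every exit, but consults it only after the exit has been labelled RLS. The label therefore controls access to the evidence that could contradict it. Someone whose RLS is rated much worse at exit can be removed from the analysis because the exit was put down to withdrawal.

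At stake is the primary endpoint of a single-arm study with no comparator, judged on a point estimate with no confidence bound. Endpoint 2 has the same structure.

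**Working it through.** **Inputs.** Formula and terms: section 17.1.3. Treatment of exits and exit scores: section 13.2. Threshold above 50%: section 17.1.5. N = 20 to 40: synopsis. The plan states no assumed rate, power or exit rate, so there is no planned figure to reproduce.

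**Step 1: how each run-in exit counts.**

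| Recorded cause | Exit CGI-I | Treatment in the plan |
|---|---|---|
| Non-RLS withdrawal | 5 or less | Removed (M) |
| Non-RLS withdrawal | 6 or 7 | Removed (M), although it meets the endpoint's failure definition |
| RLS | any | Failure (Y) |

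The second row is the problem.

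**Step 2: direction.** Let k of the M exits have CGI-I 6 or 7. None of them is in X. Keeping them as failures gives X/(N − M + k); deleting them gives X/(N − M). For any k > 0 and X > 0 the second is larger, so the bias can only be upward.

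**Step 3: size, with RLS exits as ordinary failures.** Start from X/N and move m exits from failure to M. The result passes when X/(N − m) > 1/2, that is, when m > N − 2X. The smallest such m is N − 2X + 1.

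| Start | Smallest m | Result |
|---|---|---|
| 10/20 = 50.0% | 1 | 10/19 = 52.6% |
| 15/30 = 50.0% | 1 | 15/29 = 51.7% |
| 20/40 = 50.0% | 1 | 20/39 = 51.3% |
| 9/20 = 45.0% | 3 | 9/17 = 52.9% (two give 9/18 = 50.0%, still a fail) |
| 8/20 = 40.0% | 5 | 8/15 = 53.3% (four give 8/16 = 50.0%, still a fail) |

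m = 1 requires X = N/2 exactly, so with odd N and no prior M exits one label never suffices.

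**Step 4: the formula as printed.** Moving one exit from Y to M changes the numerator as well as the denominator:
- N = 20, X = 11, Y = 1: (11 − 1)/20 = 50.0% becomes 11/19 = 57.9%.
- N = 20, X = 10, Y = 1: (10 − 1)/20 = 45.0% becomes 10/19 = 52.6%.
- N = 40, X = 20, Y = 1: (20 − 1)/40 = 47.5% becomes 20/39 = 51.3%.

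The swings are larger because Y exits never completed the assessment and so are already absent from X; subtracting them counts each one twice. That is a separate fault, so the sizes in Step 3 are the ones to rely on here.

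**Step 5: several exits (the number of exits is assumed).** On the simple count, N = 20, X = 10 with four run-in exits runs from 10/20 = 50.0% (all labelled RLS) to 10/16 = 62.5% (all labelled non-RLS). N = 40, X = 20 with six exits runs from 20/40 = 50.0% to 20/34 = 58.8%.

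**The case against.** The plan is not silent on the distinction. Section 13.2 restricts deletion to symptoms unrelated to RLS, and section 17.1.3 counts an exit in Y when RLS is the primary reason. Most of the section 6.2.1 list, such as sweating, runny nose and diarrhea, does not resemble RLS, and section 1.1 gives features that help tell RLS apart. Section 6.2.1 also expects few withdrawal symptoms. All of this narrows the ambiguity. It supplies no operational test, and it does not touch the rule that keeps a CGI-I of 6 or 7 out of the analysis.

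A reader might infer that an unblinded investigator assigns M and Y from the weekly interview or COWS. The documents do not say so. The section 17.3 form, whose responses 1 and 2 match Y and M, may be the intended source. Either way the source is open-label.

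A reader might also infer that misattribution could not be seen afterwards. That goes too far. Safety Endpoints 7 and 8 in section 17.2.1 report non-RLS withdrawal discontinuations by Phase, and exit CGI-I and IRLS are collected. A check is possible; none is planned.

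Finally, CGI-I is itself completed by the investigator or designee (section 16.9), so using it does not remove unblinded judgement. That stands, and is why the fix includes an analysis in which neither the cause nor the exit rating affects how an exit counts.

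**Conclusion.** The concern holds in a limited form. Sections 13.2 and 17.1.3 allow a subject who meets the endpoint's own failure definition to be deleted on the strength of a cause with no named assigner and no test. When that happens, Endpoints 1 and 2 are biased upward.

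The size depends on how many M exits have CGI-I 6 or 7, which the documents cannot tell us. It would be wrong to read this as one label generally deciding the trial. With RLS exits as ordinary failures, a single label reverses the result only when exactly half succeed; three are needed from 9/20 and five from 8/20. Nor do the documents show that exits will be mislabelled. The case rests on the stated rule, the overlap in symptoms, the small N and the bare 50% threshold. It is a change the sponsor should make, not a reason to reject the design.

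**What to change.** In sections 13.2 and 17.1.3:

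1. Keep the present definition of M and add a condition: an exit labelled non-RLS withdrawal stays in M only if its exit CGI-I is 5 or less. Those with 6 or 7 count as failures. No exit labelled Y may move to M.
2. Report a sensitivity analysis of Endpoints 1 and 2 with every M exit kept in the denominator as a failure. Compute it as X/N without subtracting Y; otherwise the label re-enters through the numerator. The handling of run-in exits then depends on neither the label nor an unblinded rater. For N = 20, X = 10 it gives 50.0% whatever the exits are called.
3. List each M exit with its stated reason (the section 17.3 response where available), exit CGI-I and IRLS change from baseline.

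The cost is wording in two sections, one extra analysis and one listing. Exit CGI-I and IRLS are already collected. The section 17.3 form covers only voluntary withdrawals, so its response will be missing for exits decided by the investigator; the condition in item 1 does not need it.

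The downside is that CGI-I is rated by unblinded staff and may pick up general withdrawal symptoms, so some true withdrawal exits may be counted as failures. The reported rate can only stay the same or fall. No discontinuation or dosing rule changes.

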16.9. Evaluation and study assessment schedule

The following evaluation calls and/or visits are scheduled, as outlined in Table 5 below:

Phase 1

- Evaluation 1: Enrollment, including consent, screening, device calibration, and training on device usage.
- Evaluation 2: (3-days after Eval. #1) Phone follow-up to assess NPNS use, medication use and opioid withdrawal tolerability.
- Evaluation 3: (7-days after Eval. #1) Phone follow-up to assess RLS severity, NPNS usage, and opioid withdrawal tolerability.
- Evaluation 4: (10-days after Eval #1) *Optional Evaluation, if additional time for adjusting to opioid reduction is needed.* Phone follow-up to assess NPNS usage, medication use, and opioid withdrawal tolerability,
- Evaluation 5: (14-days after Eval #1) *Optional Evaluation, if additional time for adjusting to opioid reduction is needed.* Phone follow-up to assess RLS severity, NPNS usage, and opioid withdrawal tolerability.
- Evaluation 6 (**Assessment period**): (7-days after last Eval. (3, 4 or 5)). Phone or Office follow-up to assess RLS severity (including CGI-I), NPNS usage, and opioid withdrawal tolerability. Second opioid reduction occurs, and Phase 2 of the study begins. If subject was unable to tolerate opioid withdrawal symptoms complete study exit assessments and close-out participation for the subject.

CONFIDENTIAL

All information contained in this document is confidential and is the sole property of Noctrix Health, Inc.

Any reproduction in part or whole without the written permission of Noctrix Health, Inc. is prohibited.

 NOCTRIX HEALTH	Clinical Trial Investigational Plan, Protocol CT-03 (Opioid Reduction Study)	Document #: CT-2 (Previously CT-03) Rev: 4.0 (Superseded Rev C) CC#: 720 (Previously DCO #138) Effective: 09/24/2021
---	---	---

Phase 2

- Evaluation 7: (3-days after Eval. #6) Phone follow-up to assess NPNS use, medication use and opioid withdrawal tolerability.
- Evaluation 8: (7-days after Eval. #6) Phone follow-up to assess RLS severity, NPNS usage, and opioid withdrawal tolerability.
- Evaluation 9: (10-days after Eval #6) *Optional Evaluation, if additional time for adjusting to opioid reduction is needed.* Phone follow-up to assess NPNS usage, medication use, and opioid withdrawal tolerability,
- Evaluation 10: (14-days after Eval #6) *Optional Evaluation, if additional time for adjusting to opioid reduction is needed.* Phone follow-up to assess RLS severity, NPNS usage, and opioid withdrawal tolerability.

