17.1. Efficacy

In the absence of an adjunctive treatment, a reduction in opioid dose will cause an increase in RLS symptoms. The efficacy of NPNS will be assessed by its capacity to prevent this increase in RLS symptoms. Subjects who discontinue due to nonspecific opioid withdrawal symptoms will not be included in the efficacy analysis but will be considered in the safety analysis. Efficacy endpoints will be calculated during the Assessment period except in cases of dropout during the run-in period(s); Section 13.2 describes how efficacy endpoints will be calculated in cases of dropout during the run-in period(s).

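### Sections 17.1 and 17.1.3 treat non-RLS withdrawal exits after the Run-in differently, so the primary rate depends on which rule is applied

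*Combined protocol and SAP*

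**What the plan says.** Section 17.1 states a general exclusion: "Subjects who discontinue due to nonspecific opioid withdrawal symptoms will not be included in the efficacy analysis but will be considered in the safety analysis". It does not say when in a Phase the discontinuation must occur. The next sentence places endpoint calculation in the Assessment period, apart from dropout during the Run-in, for which it refers to Section 13.2.

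Section 17.1.3 gives the formula 100% × (X − Y)/(N − M) for Endpoints 1 and 2. The terms are:
- N, everyone who started that Phase's Run-in.
- The only term that reduces the denominator: "M = Number of subjects excluded during Run-in period due to non-RLS opioid withdrawal symptoms".
- Y, those removed in the Run-in mainly because their RLS symptoms could not be tolerated.
- X, the number who complete the Assessment period without a CGI-I of 6 or 7. It carries no condition on why the subject then leaves.

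Section 13.2 has three relevant bullets. One leaves the subject's data out of that Phase's efficacy endpoints, but only where the trigger is met: "If clinically significant opioid withdrawal symptoms unrelated to RLS become intolerable during the run-in period for a given Phase". Another lets the investigator discontinue a subject at any time for excessive withdrawal symptoms. A third says that exit CGI-I and IRLS are not analysed unless RLS-related withdrawal was the primary reason for leaving.

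Section 16.9 has CGI-I rated at Evaluation 6, the end of the Phase 1 Assessment week, and says of the same visit: "If subject was unable to tolerate opioid withdrawal symptoms complete study exit assessments and close-out participation for the subject".

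Under Section 17.1.5 the study passes if Endpoint 1 exceeds 50%. The Synopsis plans 20-40 subjects in the primary study.

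**The concern.** The general rule and the formula cover different sets of subjects. Section 17.1 drops a non-RLS withdrawal exit whenever it happens; M drops it only in the Run-in. The plan expects later exits: Section 13.2 allows discontinuation at any time, Eval 6 provides for close-out, and safety Endpoints 4, 7 and 8 in Section 17.2.1 count non-RLS withdrawal discontinuations over whole Phases.

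The same subject can therefore be a non-success, a success or absent, depending on the section followed and the day of exit. With a bare 50% cut-off and a small sample, this can decide the primary result, and the choice of rule could be made after the data are known.

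**Working it through.** The plan states no exit rate, target rate or sample-size derivation, so there is no figure of its own to reproduce. Y and M are set to 0 throughout to isolate exits after the Run-in.

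**Step 1: classify the subject under each rule.**

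| Non-RLS withdrawal exit | 17.1.3 formula | 17.1 |
|---|---|---|
| During Run-in | In N and M: removed | Removed |
| During Assessment week | In N, not in M or X: non-success | Removed |
| At Eval 6, CGI-I of 5 or less | In N and X: success | Removed |

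**Step 2: effect on the rate.** With *a* Assessment-week exits, the formula gives X/N and 17.1 gives X/(N − a), which is never lower. With *e* Eval 6 exits counted in X, the formula gives X/N and 17.1 gives (X − e)/(N − e), which is lower whenever X < N.

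- One Assessment-week exit, N=20, X=10: 10/20 = 50.0% (not passed) against 10/19 = 52.6% (passed).
- One Assessment-week exit, N=40, X=20: 20/40 = 50.0% (not passed) against 20/39 = 51.3% (passed).
- Two Eval 6 exits, N=20, X=11 including both: 11/20 = 55.0% (passed) against 9/18 = 50.0% (not passed).
- Two Eval 6 exits, N=40, X=21 including both: 21/40 = 52.5% (passed) against 19/38 = 50.0% (not passed).

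At N=20 or 40 no value of X lets a single Eval 6 exit change the result. With an odd denominator one can: 11/21 = 52.4% against 10/20 = 50.0%.

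The spread is clear with two affected subjects at N=20 and the other 18 split evenly: 9/20 = 45.0% if both leave in the Assessment week, 9/18 = 50.0% if both are removed, and 11/20 = 55.0% if both leave at Eval 6 with CGI-I of 5 or less.

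**Step 3: how often the rules disagree.** Assume each subject leaves in the Assessment week for non-RLS withdrawal with probability q, and each other subject succeeds with probability p. With exits e ~ Bin(N, q) and successes s ~ Bin(N − e, p), the rules disagree when (N − e)/2 < s ≤ N/2. Summing the exact probabilities gives the percentage of trials with different pass/fail results:

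| p | N | q = 1% | q = 5% | q = 10% |
|---|---|---|---|---|
| 50% | 20 | 3.2 | 12.3 | 20.4 |
| 50% | 40 | 4.2 | 15.0 | 25.4 |
| 55% | 20 | 3.3 | 13.0 | 22.7 |
| 55% | 40 | 3.9 | 15.4 | 28.6 |
| 70% | 20 | 1.0 | 5.0 | 11.7 |
| 70% | 40 | 0.2 | 1.6 | 5.6 |
| 80% | 20 | 0.1 | 0.8 | 2.7 |
| 80% | 40 | 0.0 | 0.0 | 0.3 |

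If half of the exits fall instead at Eval 6 with CGI-I of 5 or less, the two effects partly cancel. Disagreement is then about 6-10% for p of 50-55% and q of 5-10%.

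**The case against.** The best defence is that Section 17.1 is an introductory summary and that Sections 13.2 and 17.1.3 carry the operative rule. The not-counted bullet in 13.2 is limited to the Run-in, and M matches it. On that reading an Assessment-week exit is a non-success like any other dropout after the Run-in, which is a conservative rule. The reading is possible, but the 17.1 sentence does not contain the limit, and nothing in the plan says which text governs.

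A reader might infer that the plan plainly scores withdrawal exits at Eval 6 as device successes. The documents do not support that. The 13.2 bullet on exit measures argues against using such a subject's CGI-I, although it sits in a list mainly about Run-in exits and its reach is arguable. The Eval 6 sentence also does not say whether RLS or non-RLS withdrawal is meant, and success still needs CGI-I of 5 or less. What stands is narrower: X, read alone, admits the subject, while 17.1 and arguably 13.2 do not.

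A reader might also infer that any one such subject can decide the trial, or that disagreement is typically 12-29%. The first fails for Eval 6 exits at N=20 or 40. The second needs a true rate near the cut-off and 5-10% of subjects leaving after a Run-in intended to let these symptoms resolve. Section 6.2.1 expects a low risk of withdrawal symptoms.

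**Conclusion.** The conflict is in the text and concerns the primary endpoint. It is two stated rules that differ, not a missing detail. For Assessment-week exits the consequence follows directly from N, M and X. For Eval 6 exits it holds only on a literal reading of X.

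The size depends on assumed exit rates. With 1-10% Assessment-week exits, the rules disagree in about 3-23% of trials at N=20 and 4-29% at N=40 if true success is 50-55%; in about 1-12% and 0.2-6% if it is 70%; and in under 3% at 80%. The conflict should be resolved before analysis. It does not by itself undermine an exploratory, open-label study whose rate lies well clear of 50%.

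**What to change.** Align Sections 13.2, 17.1 and 17.1.3 on one analysis rule, applied per Phase, for non-RLS withdrawal exits in the Run-in, in the Assessment week and at the end-of-Phase visit (Eval 6 or 11). Changing 17.1.3 alone would leave 13.2 silent on Assessment-week exits.

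Limiting the 17.1 sentence to the Run-in would also be consistent with M, provided that end-of-Phase exits are addressed. If the 17.1 exclusion is kept:
- define M as such exits at any time in that Phase;
- state that a subject in M cannot be in X;
- state that a Phase 2 exit does not remove the subject's Phase 1 result, which the unlimited wording of 17.1 could otherwise do;
- record at Eval 6 whether a withdrawal close-out is RLS-related or not, so that the rule can be applied.

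Removing Assessment-week exits can only raise the rate or leave it unchanged, so this choice can favour the device. Report beside it the primary rate with all such exits counted as non-successes.

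The cost is a few sentences, a slightly smaller denominator and one extra tabulation. Subject management does not change.

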17.1.1. Efficacy Endpoints

Endpoint 1 (Primary Endpoint): Percentage of subjects without a clinically significant increase in RLS symptoms (i.e. CGI-I score of 5 or less relative to baseline) during the first Phase involving an opioid dose reduction of $\geq 20\%$ relative to baseline.

Endpoint 2: Percentage of subjects without a clinically significant increase in RLS symptoms (i.e. CGI-I score of 5 or less relative to baseline) during the first Phase involving an opioid dose reduction of $\geq 1/3$ relative to baseline.

Endpoint 3: IRLS during the first Phase with an opioid dose reduction of $\geq 20\%$ relative to baseline.

Endpoint 4: IRLS during the first Phase with an opioid dose reduction of $\geq 1/3$ relative to baseline.

CONFIDENTIAL

 NOCTRIX HEALTH	Clinical Trial Investigational Plan, Protocol CT-03 (Opioid Reduction Study)	Document #: CT-2 (Previously CT-03) Rev: 4.0 (Superseded Rev C) CC#: 720 (Previously DCO #138) Effective: 09/24/2021
---	---	---

Endpoint 5: Maximal percentage reduction in opioid dose relative to baseline associated with a CGI-I score of 5 or less, averaged across subjects.

Of the 5 efficacy endpoints, only Endpoint 5 considers data during the Extension phase.

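### The formula for the primary endpoint counts each run-in RLS failure twice, so the 50% pass mark is harder to reach than the plan states

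*Combined protocol and SAP*

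**What the plan says.** Section 17.1.1 (and the Synopsis) words the primary endpoint as a plain proportion: "Percentage of subjects without a clinically significant increase in RLS symptoms", meaning a CGI-I of 5 or less, in the first Phase with a dose reduction of at least 20%. Section 17.1.5 sets the only primary pass rule: "If Endpoint 1 is greater than 50 percent, then the study will pass the Primary Efficacy endpoint".

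Section 17.1.3 gives the formula for Endpoints 1 and 2, 100% × (X − Y)/(N − M). There, N is everyone who starts run-in for that Phase, and M is those who drop out of run-in because of withdrawal symptoms that are not RLS. The term for RLS failures reads "Y = Number of subjects excluded during Run-in period primarily due to intolerable RLS symptoms". The success count, by contrast, is restricted to subjects who reach the end of the Phase: "X = Number of subjects who complete Assessment period with no clinically significant worsening". A CGI-I of 6 or 7 is what disqualifies a finisher from that count.

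Section 13.2 adds that a subject whose RLS-related symptoms become intolerable in run-in is discontinued and still counts in the efficacy endpoints for that Phase. It also says that CGI-I is taken at study exit, and that this exit score enters the efficacy analysis only when RLS-related symptoms were the main reason for leaving.

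**The concern.** X and Y cannot overlap, because membership of X requires finishing the Assessment period and membership of Y means leaving before it starts. M is taken out of the denominator; Y is not. A run-in RLS failure is thus already scored as a non-success, and the minus sign scores it a second time.

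Three things follow. The printed quantity is no longer a percentage of subjects. A run-in exit for RLS weighs twice as much as a CGI-I of 6 or 7 at Assessment, and twice as much as a run-in exit for a reason outside both Y and M, which stays in N and is counted once. And because this number is the one held against 50%, a trial that meets its primary endpoint as worded can be declared a failure as computed.

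**Working it through.** **Inputs.** The formula and the definitions of N, M, X and Y are from Section 17.1.3, the pass mark of more than 50% from Section 17.1.5, and the primary-study enrolment of 20 to 40 from the Synopsis. The plan gives no expected success rate, run-in exit rate, alpha or power, so it has no figure of its own to reproduce.

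**Step 1: the gap.** Write D = N − M.

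- Printed: 100 × (X − Y)/D
- Single count: 100 × X/D
- Difference: 100 × Y/D, which is 5.0 points per Y subject at D = 20 and 2.5 points at D = 40.

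**Step 2: what passing requires.** The printed rule (X − Y)/D > 1/2 is the same as X > D/2 + Y. The single-count rule is X > D/2.

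| D | Y | X needed, printed | as % of D | X needed, single count |
|---|---|---|---|---|
| 20 | 0 | 11 | 55.0 | 11 |
| 20 | 1 | 12 | 60.0 | 11 |
| 20 | 2 | 13 | 65.0 | 11 |
| 20 | 3 | 14 | 70.0 | 11 |
| 20 | 4 | 15 | 75.0 | 11 |
| 20 | 5 | 16 (only 15 subjects left) | – | 11 |
| 40 | 0 | 21 | 52.5 | 21 |
| 40 | 2 | 23 | 57.5 | 21 |
| 40 | 4 | 25 | 62.5 | 21 |
| 40 | 8 | 29 | 72.5 | 21 |

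Since X cannot exceed D − Y, passing is impossible as printed once D − 2Y ≤ D/2, that is Y ≥ D/4: 5 of 20, or 10 of 40.

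**Step 3: worked cases.**

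- D = 20, X = 12, Y = 2: (12 − 2)/20 = 50.0%, fail; 12/20 = 60.0%, pass.
- D = 20, X = 12, Y = 3: (12 − 3)/20 = 45.0%, fail; 12/20 = 60.0%, pass.
- D = 40, X = 24, Y = 4: (24 − 4)/40 = 50.0%, fail; 24/40 = 60.0%, pass.
- D = 20, X = 8, Y = 12: (8 − 12)/20 = −20%; 8/20 = 40%. This case is extreme, but it shows that the quantity is not bounded at zero.

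**Step 4: chance of passing under assumed rates.** Let each of the D subjects independently be a success (probability p), a run-in RLS exit (q) or another non-success (1 − p − q). Summing the exact trinomial probabilities over X − Y > D/2 (printed) and X > D/2 (single count) gives:

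| D | p | printed, q = 0.05 | printed, q = 0.10 | printed, q = 0.15 | single count |
|---|---|---|---|---|---|
| 20 | 0.60 | 0.588 | 0.449 | 0.337 | 0.755 |
| 20 | 0.70 | 0.837 | 0.706 | 0.578 | 0.952 |
| 20 | 0.80 | 0.959 | 0.884 | 0.782 | 0.997 |
| 40 | 0.60 | 0.664 | 0.464 | 0.303 | 0.870 |
| 40 | 0.70 | 0.931 | 0.801 | 0.637 | 0.994 |
| 40 | 0.80 | 0.994 | 0.960 | 0.881 | 1.000 |

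The printed statistic has expectation p − q, so more subjects do not cure the problem. At p = 0.60 and q = 0.15 it centres on 45%, and the chance of passing falls from 0.337 at 20 to 0.303 at 40.

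**The case against.** The best defence comes from Section 13.2. A subject who leaves run-in because of RLS has an exit CGI-I, and that score enters the efficacy analysis. If X were meant to include everyone with a usable CGI-I of 5 or less, subtracting Y might be meant to take such subjects back out.

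This does not rescue the formula. X, as defined, requires completion of the Assessment period. Suppose it did not, and k of the Y subjects scored 5 or less at exit and were counted. The numerator would be X + k − Y, which equals X only if k = Y, so every RLS exit would have to score 5 or less. Any who scored 6 or 7 would still be subtracted on top of being absent from X. If those k subjects were instead meant to be successes, the numerator should be X + k, with nothing subtracted.

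Some of the objection stands. The plan does not say how the exit CGI-I of Y subjects bears on the endpoint, and Sections 13.2 and 17.1.3 should be reconciled on that. The gap of 100 × Y/(N − M) is measured against X/(N − M), which treats every Y subject as a non-success; if some were to count as successes, the shortfall would be larger.

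It is also fair to say that the error works against the sponsor and cannot create a false pass, that the study is exploratory, single-arm and open-label, and that any reader given X, Y, N and M can recompute the result. These points lower the stakes. They do not make the formula agree with the endpoint.

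**Conclusion.** The formula is wrong as written. Whenever Y is above zero, the plan yields two different values for its primary endpoint, one from the wording in Section 17.1.1 and one from the formula in Section 17.1.3, and they can fall on opposite sides of 50%. Choosing between them after the data are seen would be a post hoc choice of the primary result.

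The algebra rests on the plan's definitions alone: each Y subject adds one to the number of successes needed. The pass probabilities rest on assumed rates and independent subjects. Across the grid shown, the loss runs from under 0.01 (40 subjects, p = 0.80, q = 0.05) to 0.57 (40 subjects, p = 0.60, q = 0.15: 0.870 − 0.303). If no subject leaves run-in because of RLS, there is no effect, but the plan expects such exits, since it gives them a variable and a handling rule. Endpoint 2 uses the same formula and has the same fault.

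**What to change.** In Section 17.1.3, replace the formula for Endpoints 1 and 2 with 100% × X/(N − M). State that Y subjects remain in N as non-successes, and report Y separately as a descriptive count. Add a sentence, matched in Section 13.2, saying how the exit CGI-I of those subjects is used, so that the two sections agree. If double weight for run-in RLS exits was intended, the sponsor should say so, justify it, and reword Section 17.1.1 and the Synopsis, because the result would then no longer be a percentage of subjects.

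The cost is one corrected line and one clarifying sentence, submitted as a protocol revision under Section 10.5. No new data and no extra patients are needed. The change should be made before any outcome data are analysed.
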